7.4 Device Training/Experience

At the initiation visit, the Principal Investigator and the research team will be provided with extensive training on the use of the Neurotech Vital Compact device and the itouch Sure Pelvic Floor Exerciser. The site will also be provided with training on how to train the subjects in the use of the devices in accordance with the Instructions for Use. All site and subject training will be documented.

7.5 Randomisation and Blinding

Subjects will be randomised to the Neurotech Vital Compact device or the itouch Sure Pelvic Floor Exerciser (1:1 ratio). They will know to which device they have been randomised since the two devices will be described in detail in the patient information sheet i.e., the Neurotech Vital Compact device delivers electrical stimulation through external electrodes and the itouch Sure Pelvic Floor Exerciser delivers electrical stimulation through an internal vaginal probe.

The site personnel who perform the device training at baseline and monitor the device compliance at the follow-up visits will not be blinded, but the personnel who perform the follow-up assessments will be blinded regarding device assignment.

Verification to ensure that this blinding is maintained will be assessed at the monitoring visits.

7.6 Concomitant Medication and/or Treatments

Subjects may use any medication that affects urinary output function if the medication has been used for at least 4 weeks prior to study enrolment and the medication regimen is not changed during the 12-week device treatment program

No device re-treatment will be allowed during the subject's participation in the study.

7.7 Treatment Compliance

Compliance will be assessed by reviewing the medical chart for information regarding the date and time of study visits. At each visit, information will be obtained from the devices (depending on the device) including treatment time, highest intensity reached and average intensity. In addition, subjects will be asked to complete a daily record of device use which will capture the duration of treatment and the maximum intensity reached during that session.

7.8 Unblinding/Breaking the Blind

The first course of treatment for any suspected device-related event or effect is to stop using the device. If necessary, the investigator may be made aware of the allocated treatment via the unblinded personnel at the site.

8 Study Procedures

8.1 Ethical and Regulatory Considerations

Prior to the study start relevant Institutional Research Board (IRB) approval will be obtained in writing and submitted to the Sponsor and no subjects will be recruited until a formal site initiation visit has been conducted.

This study will be conducted in compliance with:

- Study Protocol
- Applicable local IRB requirements
- US and international standards of Good Clinical Practice (FDA abbreviated IDE requirements set forth in 21 CFR 812.2(b), 21 CFR Part 50 and FDA guidance E6).
- Declaration of Helsinki as adopted by the 18th World Medical Assembly in 1964 and as revised in Tokyo (1975), Venice (1983), Hong Kong (1989), South Africa (1996), Edinburgh (2000), Washington (2002 note of clarification added), Tokyo (2004 note of clarification added), Korea (2008) and Brazil (2013).

Clinical study insurance and indemnity will be provided as required under local laws and practices.

Confidentiality of subject data will be maintained at all times. Subject anonymity will be guaranteed and all documentation relating to a subject will be kept in a secure location.

8.2 Regulatory Considerations

The Sponsor considers this study is a Nonsignificant Risk Study for the following reasons:

- In response to a written submission (Q 130879) filed by the company, giving details of the study design and the devices to be used, FDA has informed the sponsor in writing that this study may be considered a Nonsignificant Risk Study.
- The study does not meet the definitions for a Significant Risk Study.
- Non-implantable Electrical Incontinence Devices are classed by the FDA as an example of a nonsignificant risk device.
- The Neurotech Vital Compact included in this study is a Class II, CE marked medical device but has not been 510 (k) cleared by the FDA in the USA.
- The risks related to the use of the devices are minimal and the devices are being used under the supervision of the Investigator.

The study will therefore be conducted in accordance with the abbreviated Investigational Device Exemption (IDE) requirements set forth in 21 CFR 812.2(b).

The FDA also confirmed that the Neurotech Compact device can be classified as a Nonsignificant Risk device (19 September 13) since it met the definitions under 21 CFR 812.3(m).

8.3 Informed Consent

The Investigator will introduce the subject to the study by explaining the study procedures and objectives to the subject. The Investigator will then provide an information sheet describing the study, potential discomforts, risks and benefits of participation. The subject will have sufficient time to decide whether she wishes to participate in this study.

Any queries that subjects may have regarding this study will be addressed appropriately by the Investigator. Subjects will be instructed that they are free to obtain further information from the Investigator at any time, that they are free to withdraw their consent and to discontinue their participation in the study at any time without prejudice.

If the subject is willing to participate in the study, they must read, understand and sign the informed consent form. The Investigator will also sign this on the same occasion. The original copy of the signed consent form will be kept in the secure location at the study site, a copy provided to the subject and a copy filed in the medical records.

Written informed consent from the subject must be obtained before any clinical study related procedures are performed.

8.4 Study Start and Training

A summary of the schedule of events is provided in Appendix I. The study will not commence at a site until all the necessary approvals are in place and a formal study initiation visit has taken place. At the initiation visit, the monitor will ensure that all study personnel are fully aware of all study requirements and assessments. Extensive training on the use of the Neurotech Vital Compact device and the itouch Sure Pelvic Floor Exerciser will be provided as will training on how to train the subjects to use the devices correctly.

Study staff will document completion of protocol, device and study methodology training by signing the Study Training Log.

8.5 Study Recruitment

Subjects who attend the clinic for treatment of urinary stress incontinence will be approached by the Investigator to take part in the clinical study. Additionally, an approved advertisement will be made available to sites if they wish to advertise to recruit subjects into this clinical study.

8.6 Study Duration

Each subject will receive a 12-week period of treatment, which is preceded by a short period of time (2 to 4 weeks) for discussions of potential study involvement and provision of informed consent and formal evaluation of suitability for study inclusion.

Each subject will remain in the study for 14-weeks following completion of the 12 week treatment programme, therefore each subject will be involved for approximately 30 weeks.

8.7 Subject Eligibility

Once written informed consent has been obtained, the Case Report Form will be completed to document adherence to the inclusion and exclusion criteria.

Where a subject fails to fulfill any element of the inclusion and exclusion criteria, this will be documented and the signed consent form and completed inclusion/exclusion criteria retained by the Investigator. The subject will not be advanced further in the study.

When a subject is considered eligible for entry into the study, the subject will be randomized to the next available subject number (subject ID number). This number will be the unique identifier of the subject and written on each page of the Case Report Form and all other study documentation relating to the subject.

8.8 Randomisation

At the initiation visit, the designated personnel will be trained regarding how to conduct and document the randomisation of subjects enrolled into the study at that site.

The site will be provided with randomisation envelopes which will be used to allocate the devices. Access to these randomisation envelopes will be limited to the designated un-blinded personnel working on the study at the site.

When a subject has agreed to participate in the study, given informed consent, and is considered eligible with the inclusion/exclusion criteria, she will be entered into the study and only then will she be randomised to either device. The designated un-blinded personnel will train the subject according to which treatment has been allocated.

In the event of an emergency whereby it becomes necessary to know to which treatment the subject has been allocated, the investigator may be made aware of the allocated treatment via the unblinded personnel at the site. A documented procedure will be provided to the site before the study commences.

All baseline assessments must be completed prior to randomisation.

8.9 Screening Assessments – Visit 1

Each subject considered eligible for entry into this clinical study, and from whom written consent has been obtained, will have a screening assessment with the following information/procedures recorded (within 14 days of baseline assessment):

- Demographic data including height and weight.
- Medical history including details of stress urinary incontinence, previous bladder/kidney infections and any current/previous urological treatments.
- Physical examination including a detailed urological history to assess urinary symptoms and symptoms of bowel function, sexual function and pelvic organ prolapse.
- Details of all medication (over-the-counter and prescription) and dietary/herbal supplements in the previous 6 months.
- Urine pregnancy test to confirm subject is not pregnant (women of child-bearing potential only).
- Complete the Medical, Epidemiologic and Social Aspects of Aging Urinary Incontinence (MESA) Questionnaire (patient quality of life questionnaire).
- Complete a standardized stress test to evaluate amount of urine lost following a standardized bladder-filling protocol verified by ultrasound bladder scanning (provocative pad weight

test). The data from this test will not be used for analysis purposes, it is only to allow patients to practice the stress test. Further details of the stress test protocol and instructions for the Investigator and subject are provided in Appendix III.

- Record any cough or cold symptoms.
- Record any adverse events.

Prior to leaving the clinic, subjects will also be provided with the following:

- A 7-day voiding diary to complete seven days prior to the Visit 2 (baseline) appointment.
- Pre-weighed incontinence pads in a sealed bag to complete the 24-hour pad collection for three days prior to the Visit 2 (baseline) appointment.

The subject will then be asked to return the 7-day voiding diary and incontinence pads in the same sealed bag to the clinic at Visit 2. Any subjects menstruating during the three days prior to Visit 2 will also be asked to record this on the voiding diary. Any subjects who have sexual intercourse during this three day period will be asked to expel any fluid post-intercourse and also record this on the voiding diary.

8.10 Baseline Assessments – Visit 2

On the subject's return to the clinic to return the 7-day voiding diary and incontinence pads, the following information/procedures will be recorded:

- Complete the Incontinence Quality of Life Questionnaire (I-QOL) (patient quality of life questionnaire).
- Complete the Pelvic Organ Prolapse/Urinary Incontinence Sexual Questionnaire (PISQ-IR).
- Complete a standardized stress test to evaluate amount of urine lost following a standardized bladder-filling protocol verified by ultrasound bladder scanning (provocative pad weight test). This assessment will be used to determine the subject's eligibility to participate. Further details of the stress test protocol and instructions for the Investigator and subject are provided in Appendix III.
- Number of incontinence episodes/day from 7-day voiding diary.
- Number of pads used/day from 7-day voiding diary.
- Mean weight of urine leaked during three consecutive 24-hour periods at home (difference in post- and pre-weight incontinence pads) (24-hour pad weight test). Severity score will be assessed as dry (less than 2g), mild (greater or equal to 2g and less than 10g), moderate (greater or equal to 10g and less than 50g) and severe (greater than 50g) (O'Sullivan, 2004).
- Record any medication use or changes in medication since the last visit.
- Record any cough or cold symptoms since the last visit.
- Record any adverse events since the last visit.

These assessments will be performed by the designated blinded site personnel only.

8.10.1 Device Training

Subjects will be briefed by the designated non-blinded site personnel on the set-up of the Neurotech Vital Compact device or the itouch Sure Pelvic Floor Exerciser (in accordance with the allocated treatment as per the randomisation schedule). Subjects will then be asked to follow

the set-up instructions and complete a 30 minute session with the Neurotech Vital Compact device or a 20 minute sessions with the itouch Sure Pelvic Floor Exerciser in accordance with the appropriate Instructions for Use. Subjects will be at liberty to alter the intensity of the stimulation to the highest tolerable level and will be advised on the importance of achieving a strong pelvic floor contraction. Guidance will be given on the typical minimum intensity setting to achieve this effect. Subjects will be advised that it not necessary to achieve this level in their first session but that they should gradually increase the setting in their first week of use.

All of the subject's training will be documented. Subjects unable to demonstrate competent use of the Neurotech Vital Compact device or the itouch Sure Pelvic Floor Exerciser will be withdrawn from the clinical study.

The subject will be provided with the Neurotech Vital Compact device or the itouch Sure Pelvic Floor Exerciser to take home with them. Details of all devices provided, including the serial/lot numbers, will be recorded.

8.10.2 Treatment Programme Schedule – Neurotech Vital Compact device

Subjects will be advised that they should empty their bladder prior to commencing the 30 minute session of the Neurotech Vital Compact device at home.

The subjects will be instructed to use the device at home once per day, in a therapeutic position, for five days each week with two rest days taken within a 7 day week period, for the 12-week period. Each treatment cycle is fixed at 30 minutes and the device will alert the subject when the cycle is completed.

Subjects will be advised that during the 12-week treatment programme not to do any new pelvic floor exercises.

8.10.3 Treatment Programme Schedule – itouch Sure Pelvic Floor Exerciser

Subjects will be advised that they should empty their bladder prior to commencing the 20 minute session of the itouch Sure Pelvic Floor Exerciser at home.

In accordance with the instructions for use for the device, the subjects will be instructed to use the device at home once per day for the 12-week period. Each treatment cycle is fixed at 20 minutes and the device will alert the subject when the cycle is completed.

Subjects will be advised that during the 12-week treatment programme not to do any new pelvic floor exercises.

8.10.4 Prior to Leaving Clinic

Prior to leaving the clinic, subjects will also be provided with the following:

- A 7-day voiding diary to complete seven days prior to Visit 3 appointment.
- A device record form to record device use each day.
- Pre-weighed incontinence pads in a sealed bag to complete the 24-hour pad collection for three days prior to the Visit 3 appointment.

The subject will then be asked to return the 7-day voiding diary, device record and incontinence pads in the same sealed bag to the clinic at Visit 3. Any subjects menstruating during the three days prior to Visit 3 will also be asked to record this on the voiding diary. Any subjects who have sexual intercourse during this three day period will be asked to expel any fluid post-intercourse and also record this on the voiding diary

Subjects will be advised they can telephone the clinic at any time to discuss any concerns.

8.11 Assessments During 12-Week Treatment Programme – Visit 3 and Visit 4

8.11.1 Early Termination

If a subject starts treatment discontinues before completing all study visits, she is to be asked to return to the clinic to complete a Visit 4 visit as an early termination visit (if prior to that visit) or a Visit 5 visit (if after Visit 4 has taken place).

8.11.2 Telephone Contact

The subjects will be contacted via telephone at one week (Week 1) following Visit 2 to assess if there are any issues with the treatment, if they are using the device as per the Instructions for Use and to assess if there are any adverse events and/or changes to medication.

8.11.3 Timing of Visit Assessments (+/- 7 days)

Patients included in the clinical study will return for follow-up visits at 4 weeks (Visit 3) and 12 weeks (Visit 4) during the 12-week treatment programme.

8.11.4 One Week Prior to Visit

Approximately 7 days before each of the planned assessments, subjects will be contacted by telephone to remind them that their follow-up appointment is due and that they should start completing the 7-day voiding diary they have been provided which collects information on number of leaks and number of pads used per day. They will also be reminded that they should also start using their pre-packaged pads to complete the 24-hour pad collection 3 days prior to their appointment and remind them to bring the diary, pads and device back to the clinic.

8.11.5 Assessments

At each visit the following information/procedures will be recorded by the designated blinded site personnel:

- Urine pregnancy test to confirm subject is not pregnant (women of child-bearing potential only) (Week 4 only).
- Complete the Incontinence Quality of Life Questionnaire (I-QOL) (patient quality of life questionnaire).
- Complete the Pelvic Organ Prolapse/Urinary Incontinence Sexual Questionnaire (PISQ-IR) (Week 12 only).
- Complete the Patient Global Impression of Improvement (PGI-I) (Week 12 only).
- Complete a standardized stress test to evaluate amount of urine lost following a

standardized bladder-filling protocol verified by ultrasound bladder scanning (provocative pad weight test). Further details of the stress test protocol and instructions for the Investigator and subject are provided in Appendix III.

- Number of incontinence episodes/day from 7-day voiding diary.
- Number of pads used/day from 7-day voiding diary.
- Mean weight of urine lost during a three day 24-hour period at home (difference in post- and pre-weight incontinence pads) (24-hour pad weight test).
- Record any medication use or changes in medication since the last visit.
- Record any cough or cold symptoms since the last visit.
- Record any adverse events since the last visit.

At this visit the following information/procedures will be recorded by the designated unblinded site personnel only:

- Hydrogel electrodes will be checked and replaced with new electrodes if required (Neurotech Vital Compact device only).
- Data from the device will be recorded to determine stimulation parameters and duration of treatments that were completed according to the planned treatment programme. If usage information has been inadvertently erased, the device record provided by the patient may be used to provide compliance data.

At Visit 3 and Visit 4 subjects will be provided with a 7-day consecutive voiding diary and pre-weighed incontinence pads in a sealed bag to complete prior to the next visit. Subjects will be reminded to return the 7-day voiding diary and incontinence pads in the same sealed bag to the clinic at the next visit. Any subjects menstruating during the three days prior to the next visit will also be asked to record this on the voiding diary. Any subjects who have sexual intercourse during this time will be asked to expel any fluid post-intercourse and will be asked to record this on the voiding diary.

8.12 Pelvic Floor Exercises – Visit 4 Only

At Visit 4, the subjects will be provided with a set of instructions for pelvic floor exercises (Kegel exercises as outlined in Appendix IV). Subjects will be advised to perform Kegel exercises daily from 12 weeks to the 26 weeks follow-up. The device and all study-related equipment must be returned to the clinic at this visit.

8.13 Assessments Following Treatment Programme – Visit 5

The same assessments as detailed in Section 9.9.3 and 9.9.4, apart from any assessments related to the devices will be performed at 6 months (+/- 14 days) (Visit 5).

8.14 Adverse Event Reporting – All Visits

All subjects will be evaluated throughout the study for adverse events. All adverse events, including the following, will be assessed by the Investigator, and recorded in the subject Case Record Form including:

- Observed or volunteered problems
- Complaints

- Physical signs and symptoms
- Medical condition which occurs during the study, having been absent at baseline

The need to capture adverse events is not dependent upon whether or not the clinical event is associated with the use of the device. The Investigator will take all appropriate and necessary therapeutic measures required for resolution of the adverse event.

The Investigator should institute appropriate therapeutic and follow-up measures in accordance with good medical practice but should notify the monitor of such actions and record them in the subject's Case Report Form.

Further details on adverse events including definitions are provided in Section 10.0.

Each adverse event must be described in detail including the date of onset, date of resolution, severity, anticipated/unanticipated, frequency of the event (single episode, intermittent, continuous), action taken (none, medical and/or surgical), outcome, relationship to device/procedure, device details (type no./lot no./device status) and if defined as serious must be recorded. Each adverse event must be recorded separately.

Severity will be assessed using the following definitions:

Mild	Aware of sign or symptom, but easily tolerated
Moderate	Discomfort enough to cause interference with usual activity
Severe	Incapacitating with inability to work or do usual activity

The relationship to the device will be assessed by the Investigator using the following definitions:

Not Related	Evidence exists that the adverse event definitely has a cause other than the study device (e.g. pre-existing condition or underlying disease, current illness, or concomitant medication) and does not meet any other criteria listed.
Possibly Related	A temporal relationship exists between the event onset and administration of device. Although the adverse event may appear unlikely to be related to the study device, it cannot be ruled out with certainty; and or the event cannot be readily explained by the subject's clinical state or concomitant therapies.
Probably Related	A temporal relationship exists between the event onset and administration of device, and appears with some degree of certainty to be related based on known mechanism of action of the device. It cannot be readily explained by the subject's clinical state or concomitant therapies.
Definitely Related	Strong evidence exists that the device caused the adverse event. There is a temporal relationship between the event onset and administration of the device. There is strong mechanistic evidence that the event was caused by the device. The subject's clinical state and concomitant therapies have been ruled out as a cause.

9 Adverse Events and Device Deficiencies

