6.5 Monitoring for Subject Compliance

Subject compliance will be based on three assessments, namely, the level of completion of patient 7-day voiding diary, attendance at scheduled follow-up visits plus evaluation of the internal memory of the Neurotech Vital Compact device and the itouch Sure Pelvic Floor Exerciser or the Device Record (diary) to check daily use parameters and schedules.

7 Study Treatments

One device will be issued to each randomized subject in a single-blinded manner. The investigator and those administering the 1-hour provocative stress test, evaluating adverse events and reviewing diary data are to remain blinded regarding treatment assignment.

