11.5 Maintenance of Randomisation and Blinding

A randomisation schedule will be provided. The randomisation schedule is in a permuted block-format randomisation, stratified by study site, to ensure that the subject allocation at the sites remains balanced.

The Subject ID number, randomisation date and patient initials will be recorded along with the allocated treatment.

It is not anticipated that there will be any need to unblind (break the randomisation code) of any subject participating in the study because of an adverse event/adverse device effect, however, the information will be available at the site via the unblinded personnel.

One member of the investigational site team will be responsible for patient training and will consequently be unblinded to required treatment instructions for training. A different member of the team will be responsible for all other patient assessments and CRF completion.

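### The adverse event record must carry device type and lot number, which identify the arm, yet the protocol leaves that record with staff who are meant to stay blinded

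*Protocol*

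**What the plan says.** **Who stays blinded.** The opening paragraph of Protocol section 7 states: "The investigator and those administering the 1-hour provocative stress test, evaluating adverse events and reviewing diary data are to remain blinded regarding treatment assignment". Section 8.11.5 gives one list of tasks to blinded site personnel at Visits 3 and 4, and that list holds both the provocative pad test and the recording of adverse events. Section 8.10 does the same at baseline. Section 11.5 makes one team member the unblinded trainer and adds: "A different member of the team will be responsible for all other patient assessments and CRF completion".

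**What the adverse event record holds.** Section 8.14 names the investigator as assessor of all adverse events, whether or not they are associated with the device. It then says: "Each adverse event must be described in detail including the date of onset". The list that follows includes whether the event was anticipated and "relationship to device/procedure, device details (type no./lot no./device status". Causality also falls to the investigator: "The relationship to the device will be assessed by the Investigator using the following definitions".

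**When the blind may be broken.** Section 7.8 lets the investigator learn the allocation from unblinded staff where necessary. Section 11.5 does not expect an adverse event to require it.

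**Access.** Section 11.2.1 provides eCRF log-ins for blinded and unblinded personnel, but does not say which role sees or completes which adverse event fields.

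**The concern.** Participants know their device, so blinding the assessor is the only masking at the moment the primary endpoint is measured. Unblinding for an adverse event is meant to be exceptional. A routine form that asks for the device type at every event, including events unrelated to the device, would make it ordinary.

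Appendix III asks for the same examiner at each visit where possible. Device details entered for an event at the Week 1 call or the Week 4 visit could therefore be known to the person who runs the Week 12 test. For scale, the non-inferiority margin is 5 percentage points. In an arm of 90 that is 0.05 × 90 = 4.5 women, so a handful of changed responder classifications would not be negligible.

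**Working it through.** The plan states no figure here and no formula applies. The check is whether the sections can all be followed together.

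| Question | Where | Answer |
|---|---|---|
| Who must be blinded? | Protocol 7 | Investigator, stress-test staff, adverse event evaluators, diary reviewers |
| Who records adverse events at follow-up? | 8.11.5 | Blinded personnel, on the same list as the pad test |
| Who completes the CRF? | 11.5 | Someone other than the unblinded trainer |
| Who assesses events and causality? | 8.14 | The investigator |
| What must each record contain? | 8.14 | Among other items, device type, lot and status |
| Is anyone named to enter the device details? | 8.14 | No; the sentence is passive |
| Are those fields hidden from blinded users? | 11.2.1, SAP 2.4.2 | Not stated |

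**Does the field reveal the arm?** Yes. Section 7.2.1 shows two distinct products, and the Vital Compact instructions in Appendix XI give its product type as 205. A type number identifies the device at once. A lot number does so for anyone who can match it to a product.

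**Does the causality judgement reveal the arm?** Not by itself. The definitions speak of the device generically, so the judgement can be made against an unnamed study device. It is harder to make blind, because a probable relationship is one that "appears with some degree of certainty to be related based on known mechanism of action of the device", and the two mechanisms differ.

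**Does the anticipated/unanticipated field depend on the arm?** Yes. Section 9.2 lists sensitivity to the hydrogel electrodes for one device, and abdominal cramps and vaginal irritation or infection for the other. Some events can be classified only by someone who knows the device.

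**Do the exceptions cover it?** No. Section 7.8 is conditional and section 11.5 treats unblinding as unexpected, whereas 8.14 applies to each event.

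**Which tests are exposed?** Those done after the record is made. For the primary endpoint, these are events recorded from randomisation up to the Week 12 test. An event first reported at Visit 4 matters only if it is entered before that test.

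**The case against.** The strongest reply is that 8.14 does not say who enters the device details. If unblinded staff did so, every section could be honoured. The means exist: separate log-ins (11.2.1), and serial and lot numbers recorded at device issue, in a section where unblinded staff do the training (8.10.1). Section 11.5 refers to a different team member without calling that person blinded. It cannot be taken literally for every field either, because 8.11.5 has unblinded staff record device data. This stands as far as it goes: the conflict follows from reading several sections together, and a workable arrangement is possible. The protocol does not state one. Checking the blind at monitoring visits cannot supply a missing assignment of fields.

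Section 9.3 was not in the text available for this check, and the Study Specific Procedure cited in 9.4 is a separate document. If either assigns these fields, a cross-reference would settle the matter.

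A reader might infer more than the documents support:

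- **That the rules can never be reconciled.** They can, by naming the role.
- **That recording relatedness unblinds.** Type and lot number do; relatedness alone does not.
- **That nothing else in the trial is blinded.** The synopsis also blinds the statistical analysis until database lock, and SAP 2.1 settles per-protocol exclusions before unblinding. Neither protects the pad test itself.
- **That the result depends on how hard the assessor pushes.** Appendix III fixes a 132 bpm metronome, two 30-second bouts, 10 sit-to-stands, 10 coughs, 5 pick-ups, a bladder volume of at least 250 mL and a balance calibrated each assessment day. What remains is encouragement to keep pace and the force of the coughs.
- **That a set share of assessments is lost.** An assumed event rate of 30% to 50% would give 54 to 90 of 180 women. No document supplies such a rate, not every event precedes the Week 12 test, and section 7 names the investigator and the test staff separately, so they need not be the same person.

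**Conclusion.** The point holds as a gap in the blinding procedure. As written, the adverse event record can disclose the allocation to staff who are to remain blinded, for any woman with an event recorded before her Week 12 test. This rests on three readings: blinded staff complete the record (7, 8.11.5 and 11.5 together), they can see the device fields (nothing says otherwise), and some of them also run the pad test (8.11.5).

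The number of women affected cannot be derived from the documents, nor can the size or direction of any bias. The standardised test makes a large effect less likely without excluding a small one. This merits an amendment because the remedy is simple and assessor blinding is what protects the primary measurement. It does not show that the primary result would be biased.

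**What to change.** Amend Protocol 8.14 and 11.5 as follows:

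- Device type, lot number, device status and the anticipated/unanticipated classification go on an eCRF page completed by the unblinded staff member and not visible to blinded log-ins. The page links by subject ID to the serial and lot numbers recorded at device issue.
- The blinded investigator records the event, its severity, its seriousness and its relationship to the study device, without the device being named.
- The unblinding route in 7.8 stays as it is.
- Section 7.3, which gives the investigator a Device Accountability Log covering both devices, is reconciled with the investigator's blinding.

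The cost is one extra eCRF page for unblinded staff, who already have log-ins. The change does not mask an event whose nature itself points to one device, such as a reaction at the electrode site; that exposure remains, but is confined to such events.
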